There were 3 groups 1) SIT: uninterrupted sitting (control); 2) LW: sitting + 3 min bouts of light-intensity walking at 3.2 km/h every 30 min; and 3) SRA: sitting + 3 min bouts of simple resistance activities (alternating half-squats, calf raises, brief gluteal contractions and knee raises) every 30 min (see below).

Simple Resistance Activities – SRA's

Over 22 h, both LW and SRA significantly reduced mean [interstitial] glucose, time in hyperglycemia and glycemic variability (quantified via the SD of mean glucose and mean amplitude of glycemic excursions) relative to uninterrupted sitting (Table). These simple interruptions to sitting significantly reduced the time in hyperglycemia, mean glucose and glycemic variability in adults with T2D. **This approach has not been studied yet in adolescents with type 1 diabetes.**

Table (A) Participant Characteristics and (B) Effects of the Three Trial Conditions on Glycemic Control

(A) Participant characteristics		(B) Effects of the three trial conditions on measures of glycemic control over 22 h			
Characteristic	N or mean (95% CI)	Measure of glycemic control	SIT (control)	LW	SRA
Number of study participants	14 M 10 F	Time in hyperglycemia (%)	60.3 (49.2, 71.3)	37.5 (26.5, 48.6)**	26.5 (15.5, 37.6)**
Age (yr)	62.3 (64.8, 59.8)	Time in hyperglycemia (hr)	13.3 (10.8, 15.7)	8.3 (5.8, 10.7)**	5.8 (3.4, 8.3)**
BMI (kg/m ²)	33 (34.4, 31.7)	Mean interstitial glucose (mg/dl)	11 (10.2, 11.8)	9.4 (8.5, 10.2)**	8.6 (7.8, 9.4)**
HbA1c (%)	7.2 (7.5, 7)	SD of mean interstitial glucose	2.2 (2, 2.5)	1.9 (1.7, 2.2)**	1.7 (1.5, 2)**
Note: All participants were Metformin/diet controlled individuals with type 2 diabetes.		MAGE (mg/dl)	104.94 (92.11, 117.78)	85.5 (72.66, 98.34)**	76.18 (63.35, 89.02)**
SD=standard deviation; MAGE=mean amplitude of glycemic excursions. *difference from SIT ($P < 0.05$); **difference from SIT ($P < 0.001$); Analysed using multi-level mixed models, controlling for age and BMI. Data are mean (95% CI).					

IV. Research Design and Methods

In this protocol we will determine whether 'exercise snacks', alone or in combination with dietary glutamine supplementation over a period of 3 months improve glycemic control in adolescents with type 1 diabetes.

Inclusion/Exclusion Criteria:

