Twenty-four adolescents with T1D for at least 12 months, between 13-19 yr-old will be recruited after informed written consent from their parents and the youngsters themselves. We will strive to recruit patients with comparable phenotype in both groups. They will be of normal weight (BMI between 10th and <85th percentile) and will be in puberty (at least Tanner stage III breast or genitalia) with a HbA1c between 7.5 and 9%. Subjects will be on either multiple daily injections (MDI) or insulin pump therapy. They will be recruited among the ~1,000 patients with T1D followed at Nemours Children's Clinic Jacksonville. We will exclude subjects with biopsy proven celiac disease, cystic fibrosis, chronic steroid therapy, mental retardation, microalbuminuria or evidence of other diabetic complications. Subjects involved in an active exercise program or in an organized sport team will be excluded. Studies will be conducted at least 2 weeks after resolution of any intercurrent infection.

Procedures: All subjects will have a full physical exam including Tanner staging as well as waist circumference measurement. A HbA1c, will be obtained as well as fasting triglycerides. A continuous glucose monitor (CGM iPro®, Medtronic Minimed, or a DexCom ^4) will be worn blindly for 6 days and data downloaded. Subjects will then be randomized to 2 study groups of 12 patients each:

(A) an 'exercise group', in which subjects will perform daily 'exercise snacks' within 30 min before breakfast, lunch, and/or dinner or bedtime snack, along with a placebo drink;

(B) an 'exercise + glutamine group', in which subjects will receive a glutamine drink (0.25 g/kg per dose) before meals TID, and perform 'exercise snacks' before each meal.

[figure not shown]
Allocation to the exercise only or the exercise + glutamine group will be stratified according to HbA1c range (eg, 7.5-7.9%; 8.0-8.4%; 8.5-9.0%), so as to ensure the comparability of groups.

The placebo and glutamine drink will be prepared at home using measuring spoons of glutamine or placebo powder to be mixed in a calorie-free, flavored soft drink tailored to the child's individual taste. Patients, families and investigators will be blinded as to the contents of the supplement.

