-Calculations - An insulin sensitivity score (ISS) will be calculated as previously described using the SEARCH ISS model: $\log_e IS = 4.64725 - 0.02032(\text{waist, cm}) - 0.09779(\text{HbA1c, \%}) - 0.00235(\text{TG, mg/dl})$ ($R^2=0.74$ in the initial SEARCH model) [34-35]. This has been validated using the hyperinsulinemic euglycemic clamp, considered the gold standard for insulin sensitivity measures [34,35]. CGM data will be downloaded and used to calculate % blood glucose (BG) at, below or above target and the mean amplitude of glycemic excursions using a SAS program (MAGE) as previously described [17,21,22].

-Statistical Analysis and Statistical Power.

To determine whether short bouts of exercise and/or glutamine improve glycemic variability and diabetes control, we will compare the following parameters between baseline and 3 months:

- a) Changes in HbA1C
- b) Changes in MAGE
- c) Changes in % BG at target (70-180), below target (<70), above target (>180)
- d) Changes in ISS
- e) Changes in total insulin dosing (units/kg/day)

A mixed effects models and/or generalized estimating equations (GEE), which ever appropriate will be used within and between subjects and groups comparisons. Model assumptions will be checked by analyses. Significance will be established at $p<0.05$.

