-Sample Size Justification: A sample size of 24 patients is planned assuming no more than 10% attrition rate. The main judgment criterion will be the mean amplitude of glycemic excursion (MAGE, measured using CGM). In the Australian study by Dunstan et al. [36]—described above in the Preliminary results section of this application—performed in adults with type 2 diabetes, MAGE was 104.9 ± 12.8 mg/dl (mean \pm SD) in the sedentary group of patients with type 2 diabetes, vs. 76.2 ± 12.8 mg/dl—i.e., a drop by 28.7—in the group performing short bouts of resistance exercise. To the best of our knowledge, there is no earlier study of such type of exercise in adolescents with T1D published in literature. Assuming ‘exercise snacks’ will decrease MAGE to the same extent in our population of children with T1D as in adults with T2D, such reduction will amount to an effect size of $\delta/\sigma=28.7/12.8 \approx 2.24$, where δ is the expected change in MAGE ($104.9-76.2=28.7$), and σ^2 the estimated variance of MAGE ($\sigma=12.8$, calculated based on [name] et al’s data). Using equations for unpaired studies, the number (n) of subjects per group needed to detect such difference with an α risk <0.05 , and a statistical power($1-\beta$) of 80% can be estimated as: $n= 2 \times (Z_\alpha + Z_\beta)^2 / (\delta^2/\sigma^2)$ [37], where $Z_\alpha=1.96$, and $Z_\beta=0.84$, therefore $n=2 \times (1.96 + 0.84)^2 / (2.24)^2 = 2 \times 7.84/5.02=3.1$. The enrolment of 12 patients per group therefore should be amply sufficient to test our hypothesis, even if we take into account a putative 25% attrition rate.

- Future Directions: These simple and short resistance activities as it was shown in previous studies [16, 36] have significantly reduced the time in hyperglycemia, mean glucose and glycemic variability in adults with T2D. With the ubiquity of sedentary behaviors and the low adherence to structured exercise, this approach has the potential to be beneficial and practical. This interesting approach has not been studied yet with combination of glutamine in patients with type 1 diabetes.

V. Facilities Required/Physical Location of Study

This study will be performed in outpatient settings and will recruit patients who are followed at the deivision of Endocrinology at the Nemours Children’s Healthy System in Jacksonville.

VI. References

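### The main MAGE comparison states no baseline adjustment and no small-sample method for 9 to 12 patients per arm; adjusting for baseline gains precision at low to moderate baseline-to-3-month correlation, but not at every correlation.

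*Combined protocol and SAP*

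**What the plan says.** Section IV, Statistical Analysis and Statistical Power, opens with the aim "To determine whether short bouts of exercise and/or glutamine improve glycemic variability and diabetes control" and then says "we will compare the following parameters between baseline and 3 months". Changes in MAGE is the second of five listed items. The method is one sentence: "A mixed effects models and/or generalized estimating equations (GEE), which ever appropriate will be used within and between subjects and groups comparisons". Significance is set at p<0.05, and model assumptions are to be checked. No covariate, degrees-of-freedom method or variance correction is named.

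Four other statements bear on this:
- Sample Size Justification: "The main judgment criterion will be the mean amplitude of glycemic excursion".
- Procedures: allocation to two arms of 12 "will be stratified according to HbA1c range", with three ranges given as examples.
- Sample Size Justification, on attrition: "A sample size of 24 patients is planned assuming no more than 10% attrition rate". The same paragraph ends by calling 12 per arm sufficient "even if we take into account a putative 25% attrition rate".
- Procedures: CGM is worn at baseline, 1 month and 3 months, and both arms perform the exercise snacks.

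**The concern.** Two features of the method are left open, and both matter more in a trial this small.

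The first is precision. A comparison of raw changes carries the full noise of the baseline measurement. Using baseline MAGE as a covariate usually removes some of that noise and needs no new data.

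The second is the reference distribution. With 9 to 12 patients per arm, large-sample standard errors and normal critical values are not safe, and one of the two methods named (GEE) is often run with exactly those.

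Because both arms exercise, the between-arm contrast addresses glutamine only. The exercise question falls to the within-arm change, so that comparison needs a stated small-sample test as well.

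**Working it through.** **Inputs from the documents.** 12 per arm; 10% attrition leaves 12 × 0.90 = 10.8 (about 11) and 25% leaves 12 × 0.75 = 9. Two-sided 5% (Z = 1.96). Effect 28.7 mg/dl, SD 12.8 mg/dl.

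**Assumed.** Rho is not given, so it is varied from 0.3 to 0.9. MAGE is taken as normal with equal SD at both visits.

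**The plan's own figure.** n = 2 × (1.96 + 0.84)² / 2.24² = 15.68/5.02 = 3.1 per group. This reproduces. The formula is unpaired and has no baseline or correlation term.

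**Effect size used for power.** The table in section III.d gives MAGE while sitting as 104.94 (92.11, 117.78) in 24 patients and labels it mean with 95% CI. The half-width is 12.84, so the 12.8 used as an SD is a CI half-width. The implied SD is 12.84 × √24/1.96 = 32.1, or 30.4 with the t value 2.069. Then 28.7/32.1 = 0.89 and 28.7/30.4 = 0.94, so 0.9 SD is used. This is approximate because those intervals are model-based. It is an exercise effect, so for the glutamine contrast 0.9 SD is purely an assumption.

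**Variance ratio, adjusted to change score.** The change-score variance is proportional to 2(1 − rho) and the baseline-adjusted variance to (1 − rho²), so their ratio is (1 + rho)/2. Chance baseline imbalance adds a factor:
- Baseline only: 1 + 1/(2n − 4), which is 1.05 at n = 12 and 1.071 at n = 9.
- Baseline plus two stratum terms, 12 per arm, strata balanced: 1 + 1/(2n − 6) = 1.056.
- Baseline plus two uninformative stratum terms, 9 completers per arm after random dropout from 4 per stratum per arm: about 1.12 by simulation. Repeat runs differ by about 0.01 in the ratio.

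| rho | 0.3 | 0.5 | 0.7 | 0.8 | 0.9 |
|---|---|---|---|---|---|
| (1 + rho)/2 | 0.65 | 0.75 | 0.85 | 0.90 | 0.95 |
| 12 per arm, baseline only | 0.68 | 0.79 | 0.89 | 0.95 | 1.00 |
| 12 per arm, with strata | 0.69 | 0.79 | 0.90 | 0.95 | 1.00 |
| 9 per arm, baseline only | 0.70 | 0.80 | 0.91 | 0.96 | 1.02 |
| 9 per arm, with strata | 0.73 | 0.84 | 0.95 | 1.01 | 1.06 |

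The lost degrees of freedom add a little. Going from the change test to baseline plus two stratum terms raises the t critical value from 2.074 (22 df) to 2.093 (19 df) at 12 per arm, and from 2.120 (16 df) to 2.160 (13 df) at 9.

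**Between-arm power at 0.9 SD.** The change test is a noncentral t with noncentrality 0.9/√(4(1 − rho)/n) and 2n − 2 df. At n = 12 and rho 0.5 this is 0.9/√(2/12) = 2.20, giving 56%. The adjusted test is ANCOVA with baseline and two uninformative stratum terms, completers only.

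| rho | 0.3 | 0.5 | 0.7 | 0.8 | 0.9 |
|---|---|---|---|---|---|
| 12 per arm, change | 43% | 56% | 78% | 92% | 99.7% |
| 12 per arm, adjusted | 57% | 65% | 81% | 92% | 99.6% |
| 9 per arm, change | 33% | 43% | 64% | 81% | 98% |
| 9 per arm, adjusted | 42% | 49% | 65% | 80% | 97% |

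At the plan's 2.24 SD and 12 per arm, the change test already has 99.3% power at rho 0.3, so at most 1 point can be gained.

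**Error rate, conditional on one implementation.** For the baseline to 3-month change, an uncorrected sandwich z statistic equals the t statistic times √(n/(n − 1)). The true level is therefore P(|t| > 1.96 × √((n − 1)/n)), with 2n − 2 df between arms and n − 1 df within an arm.

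| n per arm | cut-off | between arms | within arm |
|---|---|---|---|
| 12 | 1.877 | 7.4% | 8.7% |
| 11 | 1.869 | 7.6% | 9.1% |
| 9 | 1.848 | 8.3% | 10.2% |

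The same contrasts with a t reference hold 5%.

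**The case against.** The strongest reply is that this is silence rather than error. A mixed model with baseline as a response and a common baseline mean adjusts implicitly, and software may supply small-sample degrees of freedom by default. The unadjusted change-score test used here as comparator is not named in the plan. That is fair, but the plan states neither safeguard and leaves the choice of method open, so the improvement is still worth specifying.

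Three stronger readings are tempting, and the documents do not support them.
- A reader might infer that the planned test has an inflated error rate. That needs GEE, an uncorrected sandwich error and a normal reference all at once. The plan commits to none of these, and a mixed model is at least as natural for a continuous outcome.
- A reader might infer that adjustment always helps and is nearly free. At 9 completers per arm with two stratum terms, it brings no gain from about rho 0.8 upward.
- A reader might infer that leaving out the strata invalidates the test. The effect is minor: it makes the test conservative if HbA1c predicts MAGE.

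It is also true that covariate adjustment does nothing for the within-arm exercise question; there the point is only the reference distribution.

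**Conclusion.** The point holds as a low-cost improvement to the analysis, not as proof that the planned test is invalid. With 12 per arm, adjustment is worth about 14 power points at rho 0.3, 9 at rho 0.5 and 3-4 at rho 0.7. With 9 completers per arm it is worth about 9, 6 and 1. These gains rest on an assumed rho, an assumed 0.9 SD glutamine effect and uninformative strata. They nearly vanish at the plan's own 2.24 SD. Most of the gain comes from baseline MAGE rather than the strata. The error-rate figures of 7.4-8.3% and 8.7-10.2% apply only to the one GEE implementation described.

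**What to change.** - **Between arms:** analyse 3-month MAGE with arm and baseline MAGE in the model, either by ANCOVA or by a mixed model of months 1 and 3 with Kenward-Roger degrees of freedom. Add the HbA1c stratum used at allocation, or HbA1c as one continuous term to save a degree of freedom if few patients complete. Settle that choice before unblinding.
- **Mixed-model form:** let the baseline and HbA1c terms vary by visit, use an unstructured covariance, and take arm at month 3 as the contrast. With complete data this equals ANCOVA with stratum (24 − 5 = 19 df). The 1-month value serves mainly to keep patients who lack a 3-month CGM.
- **GEE:** use it only with a small-sample variance correction.
- **Within arm:** test the change from baseline to 3 months with a paired t test (n − 1 df), and say which of the two comparisons is the main MAGE test. The paired test controls the error rate for the change; it does not supply a non-exercising control.

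The cost is a few lines of text and no new data. The downside is one to three degrees of freedom, and a small loss of precision if rho is about 0.8 or higher with 9 per arm.

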Complete Title of Protocol: Exercise Snacks and Glutamine to Improve Glucose Control in Adolescents with Type 1 Diabetes

NCT: NCT03199638

Date: April 24, 2015

RESEARCH PLAN

I. Specific Aims : To determine whether the sustained use of short bouts of exercise ('exercise snacks'), with or without the administration of the amino acid glutamine results in diminished glycemic variability and/or improved glucose control in adolescent with T1 diabetes.

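### Seven overlapping measures share one unadjusted p<0.05 rule under an and/or aim, and neither MAGE's main status nor a deciding contrast is written into that rule

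*Combined protocol and SAP*

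**What the plan says.** Section I (Specific Aims) asks whether exercise snacks, with or without glutamine, "results in diminished glycemic variability and/or improved glucose control". Either outcome appears to satisfy the aim.

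The Statistical Analysis and Statistical Power part of section IV says "we will compare the following parameters between baseline and 3 months" and gives five lettered items. Item c) holds three variables, "Changes in % BG at target (70-180), below target (<70), above target (>180"), so the list contains seven: HbA1c, MAGE, three CGM percentages, the insulin sensitivity score (ISS) and insulin dose. Mixed models or GEE are to serve for comparisons both within and between groups. The decision rule is one sentence: "Significance will be established at" p<0.05. No measure is ranked, no test order or adjustment is given, and no contrast is singled out.

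The Sample Size Justification that follows adds "The main judgment criterion will be the mean amplitude of glycemic excursion" and sizes the study on MAGE alone, with an unpaired two-group formula.

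Under Procedures, both arms of 12 perform exercise snacks. They differ only in receiving glutamine or placebo.

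**The concern.** The aim, the list of measures and the significance rule do not fit together. The sample-size paragraph gives MAGE a special status, but the analysis rule treats it as item b) of an unranked list. The status also attaches to a variable and not to a test: MAGE can be tested within the exercise arm, within the exercise-plus-glutamine arm and between the arms, each at 0.05.

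If MAGE alone decides, the glucose-control half of the aim has no decision rule. If MAGE does not decide alone, the error rate for the aim is uncontrolled. With 24 patients, a chance result on HbA1c, a CGM percentage or another listed measure could then be reported as meeting the aim. This has to be settled before the data are seen.

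**Working it through.** **Plan's own figure.** With δ = 28.7 and σ = 12.8 mg/dl, Zα = 1.96 and Zβ = 0.84 (Sample Size Justification), n = 2 × (1.96 + 0.84)² / (28.7/12.8)² = 3.12 per group. The plan prints 3.1, so the arithmetic reproduces. This does not endorse the inputs. The figure covers one two-sided test of one measure at 0.05. The plan states no error rate for the set of measures.

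**Inputs.** Twelve per arm (Procedures); two-sided 0.05 per test (the threshold is in Statistical Analysis, and the sidedness is inferred from Zα = 1.96); seven measures; up to three contrasts per measure (change within each arm, difference between arms). The documents give no correlations among the measures, so common pairwise values of 0 to 0.5 are assumed, with higher values as a sensitivity check.

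**Step 1: independence bound, one contrast.**
- Either direction: 1 − 0.95⁷ = 30.2%.
- Favourable direction only: 1 − 0.975⁷ = 16.2%. The like-for-like single-test reference is 2.5%, not 5%.

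These are upper markers, because the measures overlap. The three CGM percentages sum to 100, so they carry two pieces of information, and ISS is computed partly from HbA1c.

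**Step 2: simulated null trials, t-tests, % at target derived from the other two percentages.** The relative weight of % below and % above target is also an assumption.

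| Assumed correlation | Between-arm, either direction | Adding within-arm tests, either direction | Adding within-arm tests, favourable only |
|---|---|---|---|
| 0 | 27% | 53% | 35% |
| 0.3 | 25% | 49% | 31% |
| 0.5 | 22% | 44% | 26% |

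The between-arm rate in the favourable direction alone is about 11-15% over the same range. Building ISS partly from HbA1c gives 20-27% either direction and 10-14% favourable for the between-arm tests. Across these variants the ranges are about 20-28% and 10-15% between arms, and about 42-54% and 25-35% once within-arm tests are added.

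**Step 3: sensitivity.** Stronger correlation lowers the rates. For seven measures with a common correlation and no derived measure, the between-arm rates are 19% (either direction) and 9% (favourable) at 0.7, and 12% and 6% at 0.9.

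**Step 4: MAGE alone.** The two within-arm tests use different patients, so together they give 1 − 0.95² = 9.75%. Three independent tests would give 1 − 0.95³ = 14.3%. The between-arm test shares data with the other two, and simulation puts the total at about 12% in either direction.

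**The case against.** The strongest reply is that the plan does prespecify a primary outcome. The Sample Size Justification names MAGE, directly after the significance rule and within the same combined document. On that reading a single MAGE contrast keeps its 5% level. No sentence says that any one significant measure is enough: the p<0.05 sentence is a threshold, not a success rule. In the analysis section's own opening, *and/or* joins the interventions, while the outcomes are joined by *and*. ISS and insulin dose are also not direct measures of variability or glucose control. With only the five glycaemic measures, the between-arm rates fall to 16-20% in either direction and 8-11% in the favourable direction.

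Much of this stands. A reader might infer that the plan expressly lets any nominal result count as success. It does not say so; it leaves the question open, and the *and/or* between outcomes appears in the Specific Aims. A reader might also take a figure of 22-30% as the chance of a false claim of benefit from the between-arm tests. That is not supported: such figures count worsening as well as improvement, and the upper end requires seven independent tests, which these measures cannot be.

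What does not stand is that naming MAGE settles the matter. The label reaches neither the aim nor the analysis rule, and it does not say which of three MAGE comparisons decides. Nor can the within-arm tests be set aside as incidental. Both arms exercise, so baseline-to-3-month change is the only comparison the plan offers on exercise itself.

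**Conclusion.** The concern holds as a conditional statement. If any nominal p<0.05 among the listed measures may support the aim, the false-positive risk is several times the single-test level: about 20-28% in either direction between arms, and about 10-15% in the favourable direction against 2.5%. Counting the planned within-arm tests raises these to about 42-54% and 25-35%.

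The figures rest on 12 analysed per arm, assumed correlations of 0-0.5 and the sum-to-100 constraint. They describe any listed measure, not MAGE. For MAGE the risk is 5% if one contrast is fixed in advance and about 12% if all three remain open. The documents support neither a claim that the plan lacks a main criterion nor a claim that its primary error rate is necessarily inflated. They show that the main criterion is not connected to the decision rule, and that its contrast is missing.

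**What to change.** In the Statistical Analysis section:

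1. State that the conclusion rests on MAGE, and name the contrast for each part of the aim. The randomised between-arm difference in MAGE change at 3 months, two-sided 0.05, is the confirmatory test. Say plainly that it tests the addition of glutamine only. The 28.7 mg/dl effect used for sample size compares resistance activity with uninterrupted sitting, so it should not be presented as the power basis for this contrast.
2. Report the baseline-to-3-month MAGE change as the evidence on exercise snacks, labelled uncontrolled and non-confirmatory. If the sponsor wants it confirmatory, make it one pooled test sharing the 0.05 with the glutamine test, for example by Holm or a fixed order. That controls the error rate but does not supply a no-exercise comparator.
3. Label HbA1c, the CGM percentages, ISS and insulin dose as secondary, report estimates with 95% CIs, and make no efficacy claim from a nominal p<0.05 on any of them. Formal adjustment among these measures is optional once this is stated.
4. Reword the *and/or* aim to match the rule.

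No visits, measurements or patients change. The real costs are that nominal secondary results can no longer be claimed as efficacy, and that the plan must say openly that its randomised comparison does not test exercise.

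### The claim that 12 per group is ample even after 25% attrition rests on a confidence-interval half-width used as a standard deviation; on the SD the table suggests, the shortfall exists with no attrition at all

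*Combined protocol and SAP*

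**What the plan says.** The relevant text is the Sample Size Justification in section IV. It opens with the planned number and a ceiling on losses: "A sample size of 24 patients is planned assuming no more than 10% attrition rate". It names the endpoint: "The main judgment criterion will be the mean amplitude of glycemic excursion (MAGE, measured using CGM"). It then takes MAGE values from the study of interrupted sitting in adults with type 2 diabetes, labels them mean ± SD (104.9 ± 12.8 against 76.2 ± 12.8 mg/dl), forms an effect size of 28.7/12.8 ≈ 2.24, and obtains 3.1 subjects per group from the normal-approximation formula for two independent groups. It closes: "The enrolment of 12 patients per group therefore should be amply sufficient to test our hypothesis", and extends this to heavier losses, "even if we take into account a putative 25% attrition rate". No attrition term enters the formula and no evaluable number is given.

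The source data are in section III.d, table (B). The MAGE entry for uninterrupted sitting is "104.94 (92.11, 117.78", and the table note says that the entries are means with 95% confidence intervals, analysed by multi-level mixed models. Table (A) gives 14 male and 10 female participants.

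On the comparison, the Procedures in section IV state: "Subjects will then be randomized to 2 study groups of 12 patients each". Both groups perform exercise snacks; they differ in glutamine versus placebo drink.

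**The concern.** A paragraph that returns 3.1 per group makes any plausible loss look harmless, and that is why the plan can extend its assurance to 25% attrition. The assurance is only as good as the SD behind it. A 95% interval for a mean of 24 people has a half-width well under the SD, so using the half-width as the SD inflates the effect size and shrinks the required number by the square of that error.

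MAGE is the main criterion. If power is near one half rather than above 99%, a null result from 18 to 24 patients would be read against a promise of ample power that the design does not keep.

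**Working it through.** **Inputs.** From the Sample Size Justification: δ = 28.7 mg/dl, stated SD 12.8, Zα = 1.96 (so two-sided 0.05), Zβ = 0.84, 12 per group, losses of 10% and 25%. From table (B) in section III.d: MAGE intervals 92.11–117.78, 72.66–98.34 and 63.35–89.02. From table (A): n = 14 + 10 = 24.

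**1. The plan's figure reproduces.** n = 2(1.96 + 0.84)²/2.24² = 2 × 7.84/5.02 = 3.1 per group. The formula is applied correctly to its inputs. (At so small a number the normal approximation is optimistic: at d = 2.24 the t-test has 75% power with 4 per group and 87% with 5, so 5 are needed. Against 9 to 12 available this is immaterial.)

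**2. Evaluable numbers.** 24 × 0.90 = 21.6, or 10.8 per arm. 24 × 0.75 = 18, or 9 per arm.

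**3. Attrition on the plan's own SD.** With SD 12.8, t-test power for 28.7 is 99.95% at 12, 99.9% at 10.8 and 99.4% at 9 per arm. Losses would have to exceed 1 − 5/12 = 58% before even the t-based requirement failed. On these inputs neither attrition rate matters.

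**4. Where 12.8 comes from.** Half-widths of the three MAGE intervals:
- sitting: (117.78 − 92.11)/2 = 12.84
- light walking: (98.34 − 72.66)/2 = 12.84
- resistance activities: (89.02 − 63.35)/2 = 12.84

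The quantity called an SD is the half-width of a 95% confidence interval.

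**5. Recovering an SD.** Assume a simple interval for a mean of 24 people, so half-width = c × SD/√24:
- c = 1.96: SD = 12.84/1.96 × √24 = 32.1
- c = 2.069 (t, 23 df): SD = 12.84/2.069 × √24 = 30.4

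The effect size falls from 2.24 to 28.7/30.4 = 0.94 or 28.7/32.1 = 0.89.

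**6. Power and detectable difference.** Power comes from the noncentral t with 2n − 2 df and λ = δ/(SD√(2/n)); for example, at n = 12 and SD 30.4, λ = 28.7/12.41 = 2.31. The standardised difference detectable with 80% power is 1.197 at 12 per arm, 1.269 at 10.8 and 1.407 at 9; multiplying by the SD gives mg/dl.

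| Evaluable per arm | Power for 28.7, SD 12.8 | Power for 28.7, SD 30.4 / 32.1 | Detectable at 80% power, SD 30.4 / 32.1 |
|---|---|---|---|
| 12 (no loss) | >99% | 60% / 55% | 36.4 / 38.4 mg/dl |
| 10.8 (10% loss) | >99% | 55% / 51% | 38.6 / 40.7 mg/dl |
| 9 (25% loss) | >99% | 47% / 43% | 42.8 / 45.2 mg/dl |

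Eighty per cent power for 28.7 mg/dl needs 19 evaluable per arm (SD 30.4) or 21 (SD 32.1).

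**7. How large the SD may be before the claim fails.** For 80% power at 28.7 mg/dl the SD must not exceed 28.7/1.197 = 24.0 with 12 per arm, or 28.7/1.407 = 20.4 with 9 per arm.

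**The case against.** A reader might infer that the paragraph contradicts itself by planning on 10% attrition and then claiming sufficiency at 25%. The wording does not support that. The first rate is stated as an upper limit for planning and the second is introduced as a harsher hypothetical. The sufficiency claim has one definite basis, 3.1 per group, and 9 per arm is about three times that. Neither rate is sourced and the evaluable numbers are left unstated, but settling on a single rate would change neither the enrolment nor the conclusion.

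It can also be said that, with the larger SD, attrition is not the cause of the shortfall, since power is already 55–60% with nobody lost. That is right. The defect is the SD; attrition only moves the result within a range that is too low throughout.

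The strongest technical objection concerns the conversion in step 5. The source was a crossover study analysed by mixed models adjusted for age and BMI, and three practically identical half-widths suggest model-based standard errors rather than separate raw SDs. The 30.4–32.1 is therefore an approximation, and the documents do not establish it as the SD of MAGE, still less as the SD in adolescents with type 1 diabetes or of a change over 3 months. This limits the precision of the power figures. It does not rescue 12.8, which the table identifies as an interval half-width whatever the model.

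Finally, counting completers may be somewhat severe: CGM is repeated at one month and mixed models or GEE are planned, so a patient lost later could still contribute data. Even full retention gives only the first row of the table.

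**Conclusion.** The sufficiency claim is not supported as written. The mislabelled SD follows directly from the plan's own table and needs no assumption. Its size does: taking the intervals as simple ones for 24 people, the SD is about 2.4 to 2.5 times the value used (30.4/12.8 and 32.1/12.8), and power for 28.7 mg/dl is between 43% and 60% across no, 10% and 25% loss, instead of above 99%.

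One further limit applies. The 28.7 mg/dl is the difference between resistance activities and uninterrupted sitting, whereas both randomised arms here exercise. A reader might take the 43–60% as this trial's power to detect a glutamine effect. The documents give no expected glutamine effect on MAGE, so the figures support only a statement of the between-arm difference that the trial could detect.

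**What to change.** Keep enrolment at 24 and rewrite the Sample Size Justification:

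- Describe 12.8 mg/dl as the half-width of a 95% confidence interval, and replace it with the SD derived from it (about 30.4–32.1 mg/dl), stating the simple-interval assumption and that the source used mixed models in a crossover study.
- Remove the 3.1 per group and the statement that 12 per group is ample. In their place give the t-based between-arm MAGE difference detectable with 80% power: about 36–38 mg/dl at 12 per arm, 39–41 at 10% loss (about 21–22 patients) and 43–45 at 25% loss (18 patients).
- Keep both attrition rates, labelling 10% as the planning figure and 25% as a sensitivity case.
- State that 28.7 mg/dl is an exercise-versus-sitting difference and is not offered as the expected glutamine-versus-placebo effect.

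The cost is one rewritten paragraph and a less favourable statement of what the trial can show. No patient numbers, visits or procedures change.
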